Complete eligibility checklist	x					
Complete Patient History Form: HX100	x					
Complete ASES Assessments: ASES100	x		х	x	х	х
Complete SANE Assessment: SANE100			x	x	x	х
Complete Constant Score Form: CST100	х		X**	x	х	х
Randomize Patient		х				
Record Operative Details: OP100		х				
Collect Radiographic Images (AP Int., AP Ext, and Axillary Views)			x	x	x	x
Protocol Deviation Form: PD100	As needed	As needed	As needed	As needed	As needed	As needed
Complete Adverse Event Form: AE100 and/or Serious Adverse Event SAE100	As needed	As needed	As needed	As needed	As needed	As needed
Complete patient Withdrawal Form: WD 100		As needed	As needed	As needed	As needed	As needed
Complete Device Revision/Removal: RR100			As needed	As needed	As needed	As needed

Each follow-up visit time point will be determined based on the date of surgery.

** At the 6 week interval, in order to protect the subscapularis repair, the strength and ROM sections are not to be completed by sites.

*** Annual follow up will continue until study closure or until the last enrolled patient reaches their 2 year follow up window.

BILATERAL PATIENTS

A patient undergoing staged bilateral surgery must sign a consent form **for each study procedure**. Each study shoulder will be randomized separately. Bilateral patients will be required to wait at least 9 months between procedures for the purposes of the study.

Patients with staged bilateral study implants will require two ASES, Constant Score, and SANE assessment forms to allow individual assessment of each operative side over the course of the study. Patients must be instructed to assess each shoulder individually, i.e., only record right-shoulder pain levels on the CRF for their right shoulder and only report left shoulder pain on the CRF for the left shoulder.

SCHEDULE OF FOLLOW-UP ASSESSMENTS

Post-operative clinical and radiographic evaluations will be performed according to the following schedule, with the associated visit windows:

- 6 weeks (± 2 weeks)
- 3 months (± 2 weeks)
- 1 year (± 2 months)
- 2 years (± 2 months)
- Annually thereafter* (± 2 months)
- * Until all patients reach the 2-year visit window or the study is closed

ASSESSMENT PARAMETERS AND METHODS

Pre-Operative Visit - Medical History, Demographic Data and Patient Eligibility

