Balanced, blocked randomization (1:1, Investigational: Control) will be implemented. Randomization will be per shoulder, and each shoulder will count as a separate case toward the total sample size. In the event that a screen failure occurs post-randomization, randomization will not be reassigned and this shoulder will not count toward the overall sample size. Randomization will continue with the next shoulder enrolled as previously described until the minimum sample size is reached in both treatment groups. Randomization will be blocked by site, and each site will receive separate randomization plans using a predetermined block size that will remain undisclosed to the sites.

SAMPLE SIZE CALCULATION INITIAL SAMPLE SIZE CALCULATIONS AND ASSUMPTIONS

The primary objective of this study is to show that the Investigational device is non-inferior to the Control device with respect to three co-primary endpoints at 22+ months. The sample size for each endpoint was calculated, and the largest chosen as the sample size for this study. The endpoint requiring the largest sample size was Radiographic Success; therefore the sample size for this study will be the one described immediately below. For reference, the sample size for the other two endpoints is shown as well.

Radiographic Success

Non-inferiority sample size calculations were implemented in nQuery Advisor 7.0 software using a 1:1 ratio of Investigational to Control subjects. This software uses methodology as described in a text by Farrington and Manning⁵.

The sample size needed to obtain 90% power for testing for non-inferiority of the investigational device to the control device with regard to radiographic success was calculated as follows:

⁵ Farrington and Manning. "Test statistics and sample size formulae for comparative binomial trials with null hypotheses of non-zero risk difference for non-unity relative risk". *Statistics in Medicine* 9(1990) pp 1447-1454.

Definitions:

 p_I : Proportion of Radiographic success in the Investigational treatment group

 p_C : Proportion of Radiographic success in the Control treatment group.

δ: Non-inferiority margin. Lower 95% confidence bound for difference in proportions of clinically successful subjects at 22+ months (Investigational – Control) must be greater than -δ.

For a specified constant, $0 < \delta < 1$, the hypotheses of non-inferiority are:

 $H_0: \ p_I - p_C \le -\delta \ vs. \quad H_A: \ p_I - p_C > -\delta.$

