Subjects who have been randomized to the Investigational or Control group in this study comprise the All Enrolled population. The co-primary endpoints will be analyzed for the All Enrolled population and the results will be compared to the primary analyses performed on the Analysis population to determine whether the results of this analysis are consistent for both populations. For patients in the All Enrolled Population who are missing data necessary for the determination of any of the co-primary endpoints at 22+ months, data will be imputed as described below in the section "Sensitivity Analyses."

ANALYSIS POPULATION

Subjects who have been randomized to the Investigational or Control group in this study and who have complete data for a primary endpoint collected per the protocol at 22+ months or who have had a revision or removal at or before 26 Months will be included in the Analysis Population. This is the population that will be used in the primary study analysis and determination of study success. Those subjects who are missing their primary endpoint at 22+ months will be included as part of the All Enrolled population described above. Subjects with protocol deviations will be analyzed on an individual basis to determine if they will be included in the Analysis Population.

MISSING DATA AND SENSITIVITY ANALYSES

Data will be considered "missing" for a given primary endpoint if this endpoint cannot be calculated or is not available for a subject in the All Enrolled population. If the subject has had a

device failure at any point on or prior to their 22+ month outcome, they will *not* be considered as missing data for the Absence of Revision/Removal/UADE endpoint, as this endpoint is cumulative. A subject who has had a revision or removal prior to two years will be considered a radiographic failure at the 22+ month time point for purposes of the primary analysis. When possible (i.e. the subject is seen by a study investigator in a non-emergency situation and collection of the data will not cause undue burden), ASES scores will be collected for these cases before the revision is performed in order to prevent these patients from missing knee scores in the primary efficacy analyses.

Sensitivity analyses will examine the sensitivity of the results to missing values of the primary outcomes using the following analyses:

Outcome Type	Analysis Description	
Binary	Tipping Point Analysis: Missing observations are replaced with	

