The association between the primary endpoints and device group at 22+ months across investigators will be examined using either an analysis of variance model (for ASES score) or the Breslow-Day test for homogeneity of odds ratios (for Radiographic Success and Absence of Revision/Removal/UADE). These tests for interaction will use a p-value of 0.10. If there is no evidence of treatment *center interaction ($p \ge 0.10$) for a particular outcome, data will be pooled across centers for that outcome. If p < 0.10, then this outcome for each site will be examined graphically to assess site dependency as well as whether or not a qualitative interaction exists. Further, the sites contributing to this interaction will be examined, and if necessary, a stratified analysis will be conducted and results compared to overall study results to assess consistency.

In addition, the association between device group and the primary endpoints for unilateral and bilateral subjects will be examined using either an analysis of variance model (ASES) or the Breslow-Day test for homogeneity of odds ratios (Radiographic Success and Absence of Revision/Removal/UADE). As before, a significant p-value (p <0.10) for a particular outcome indicates heterogeneity in that outcome for unilateral and bilateral subjects; if this occurs, that outcome for each group will be examined graphically and descriptively to assess these differences. Primary outcomes for unilateral and bilateral subjects will also be compared using a Fisher's exact test (Radiographic Success and Absence of Revision/Removal/UADE) or a pooled t-test (ASES). If p<0.10 for the two-way comparison or the test for interaction, the

bilateral subjects will be compared as a separate group for that outcome, and additional unilateral subjects may be enrolled (via IDE supplement/protocol amendment) in order to protect statistical power of the primary study analysis.

PROTOCOL DEVIATIONS

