BASELINE CHARACTERISTICS

Subjects in the Investigational and Control study groups will be compared regarding a list of baseline items, including preoperative ASES and Constant Scores, demographics (age, gender, and primary diagnosis), medical history, and comorbidities.

EFFICACY EVALUATIONS

Primary Endpoint

The confidence intervals used in the analysis of the binary primary endpoints (Radiographic Success and Absence of Revision/Removal/UADE) will be 1-sided, 95% confidence intervals for the difference between proportions in two independent samples. They will be calculated using the Wald method as based on a normal approximation to the binomial, as follows:

$$(p_C - p_I) + z_\alpha \sqrt{SE_C^2 + SE_I^2}$$

Where

 p_{C} = proportion of success in the Control group, p_{I} = proportion of success in the Investigational group, α = 0.05, and

$$SE_C = \sqrt{\frac{p_C(1-p_C)}{n_C}}$$
 and $SE_I = \sqrt{\frac{p_I(1-p_I)}{n_I}}$

The confidence interval used in the analysis of the continuous primary endpoint (ASES Score) will be a 95% confidence interval for the difference between means in two independent samples. They will be calculated using the normal distribution, as follows:

$$(\overline{x}_C - \overline{x}_I) + z_\alpha \sqrt{\frac{s_C^2}{n_C} + \frac{s_I^2}{n_I}}$$

Where

 x_{C} = mean ASES score in the Control group,

 $\overline{x_{I}}$ = mean ASES score in the Investigational group,

 $s_{\scriptscriptstyle C}$ = standard deviation of the ASES scores for the Control group,

 s_{T} = standard deviation of the ASES scores for the Investigational group, and

 $\alpha = 0.05$

Secondary Endpoints

Secondary outcomes include the ASES score, SANE score, Constant score, and radiographic endpoints at 6 weeks, 6 months, 1 year, and 2 years separately. These outcomes will be compared for Investigational and Control groups at each time point.

Exploratory Analyses14

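### The primary ASES interval is valid but omits pre-operative ASES and site, and the plan leaves open whether bilateral shoulders stay in the analysis that decides success

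*Combined protocol and SAP*

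**What the plan says.** **ASES interval.** Under Efficacy Evaluations, Primary Endpoint, the ASES interval "will be a 95% confidence interval for the difference between means in two independent samples". The formula is the raw difference in means plus a normal quantile times the unpooled standard error. It is written as Control minus Investigational, which is the mirror image of the one-sided lower bound against −9.5 in Primary Statistical Hypotheses.

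**Pre-operative ASES.** In Table 1 of the protocol, the row "Complete ASES Assessments: ASES100" is marked at the pre-operative visit and at every follow-up. In the analysis, the baseline score appears only in the comparison of baseline characteristics and as a covariate in the Exploratory Analyses.

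**Site.** Randomization Details says "Randomization will be blocked by site, and each site will receive separate randomization plans". In the analysis, site enters through a treatment-by-centre test at 0.10. If that test is positive, the sites are examined and "if necessary, a stratified analysis will be conducted and results compared to overall study results to assess consistency".

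**Gender.** Section C, Gender, allows a gender-adjusted primary analysis if the arms differ in sex ratio. This is the only covariate with a route into the primary analysis.

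**Bilateral shoulders.** Randomization Details says "each shoulder will count as a separate case toward the total sample size". The Analysis Population is defined without reference to laterality, and the SAP says of it: "This is the population that will be used in the primary study analysis and determination of study success". Tests for Interaction then sets two unilateral/bilateral tests per co-primary endpoint. If either gives p<0.10, "bilateral subjects will be compared as a separate group for that outcome". The same section goes on to allow an extension of recruitment in that event: "additional unilateral subjects may be enrolled (via IDE supplement/protocol amendment) in order to protect statistical power of the primary study analysis".

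**The concern.** The plan collects the same score before surgery and blocks randomisation on site, then uses neither in the interval that decides the ASES endpoint. That can leave the interval wider than it need be, which matters mainly if the investigational device is truly a little worse.

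The second matter concerns which shoulders decide. If bilateral shoulders were set aside after a laterality test, the deciding population for an endpoint would be chosen from that endpoint's own 22+ month results. At stake are the 5% error rate and the power for radiographic success, which sets the sample size and has no reserve.

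**Working it through.** **1. The plan's own figure.** Inputs from Sample Size Calculation: SD 19, margin 9.5, one-sided α 0.05, power 90%.

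- n = 2 × (1.645 + 1.282)² × (19/9.5)² = 68.5, so 69 per arm by the normal approximation.
- The noncentral-t version gives 70, as the plan states, and 70/0.85 = 82.4 gives the stated 83.
- Radiographic success sets the actual size: 112 evaluable and 132 enrolled per arm.

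**2. Unadjusted interval at 112 per arm.**

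- SE = 19 × √(2/112) = 2.539. Half-width = 1.645 × 2.539 = 4.18.
- Power at true difference d is Φ((9.5 + d)/SE − 1.645).
- At d = 0: Φ(3.742 − 1.645) = 98.2%. At d = −3: Φ(2.560 − 1.645) = 82.0%.

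**3. With adjustment.** Baseline at correlation r multiplies the SE by √(1 − r²). The documents give no r and no site intraclass correlation (ICC), so both are assumed. The last two columns are simulated half-widths for the full ANCOVA: 20,000 runs per setting, 17 equal sites balanced within site, and a t quantile on 224 − 19 = 205 df.

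| r | Half-width, baseline only | Power, d = 0 | Power, d = −3 | With site, ICC 0 | With site, ICC 0.05 |
|---|---|---|---|---|---|
| unadjusted | 4.18 | 98.2% | 82.0% | – | – |
| 0.1 | 4.16 | 98.3% | 82.3% | 4.19 | 4.08 |
| 0.2 | 4.09 | 98.5% | 83.3% | 4.12 | 4.02 |
| 0.3 | 3.98 | 98.9% | 85.1% | 4.02 | 3.90 |
| 0.5 | 3.62 | 99.6% | 90.5% | 3.65 | 3.52 |

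If neither baseline nor site predicts the outcome, the ANCOVA is about 1% wider (4.21 against 4.17, simulated). The entry limit of ASES ≤ 40 restricts the baseline range, so a low r is plausible.

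**4. Validity of the unadjusted interval, at a true difference of −9.5.**

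- With no site effect, using z in place of t on 222 df gives 5.07%.
- Simulated error is 4.5–5.2% with 0–20% of shoulders from bilateral patients, within-patient correlation up to 0.8, and ICC 0 or 0.05.
- At an assumed ICC of 0.10 it is about 4.4%, against about 5.0% for ANCOVA.

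**5. How often the laterality trigger fires by chance.** There is no true laterality effect, and bilateral shares of 5, 10, 20 and 30% are assumed because the documents give none.

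- ASES: two 10% tests, if independent, give 1 − 0.9² = 19%. Simulation with within-patient pairing gives 24–27%.
- Radiographic success: 8, 11, 16 and 18%, simulated with shoulders independent.
- Revision/removal/UADE: 7, 9, 14 and 17%, on the same basis.

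**6. If bilateral shoulders then left the deciding analysis.**

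- ASES type I error: with f the bilateral share, z(unilateral) = √(1 − f) × z(all) + √f × z(interaction). The laterality main-effect test is taken as an independent 10% trigger. Error is 5.0% if all shoulders decide, and 5.1, 5.3, 5.5 and 5.8% if unilateral shoulders decide after a trigger.
- Radiographic power is Φ(0.10/√(2 × 0.93 × 0.07/n) − 1.645). At n = 112 this is Φ(2.933 − 1.645) = 90.1%. At n = 106, 101, 90 and 78 it is 88.7, 87.3, 83.8 and 78.9%.
- These powers apply only when the trigger has fired and nobody has been replaced. Weighted by the chance trigger rates for that endpoint, the average loss is about 0.1, 0.3, 1.0 and 2.0 points.

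**The case against.** **On adjustment.** An unadjusted prespecified interval is a legitimate choice, and ASES is not the limiting endpoint. If the three endpoints were independent, joint power at 112 per arm would be 0.901 × 0.963 × 0.982 = 85.2%. Adjustment at r = 0.2–0.3 lifts it only to 85.5–85.8%. With r = 0.1 and no site differences, the site-adjusted model is very slightly worse (4.19 against 4.18). An adjusted estimate will also be available from the exploratory regression. All of this stands, and it keeps the point small. It does not remove it: an exploratory result cannot decide success, and the data are already being collected.

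A reader might infer that the unadjusted interval is invalid, or that it is conservative in general. Neither follows. Its error is about nominal if sites do not differ and mildly below nominal only if they do.

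**On bilateral shoulders.** Tests for Interaction never says that they leave the Analysis Population, and the separate comparison can be read as an addition. That also stands: the conflict is by implication. Against the milder reading, if bilateral shoulders stayed in, no power would be lost and extra unilateral enrolment would have nothing to protect. The replacement enrolment is a real mitigation, though it is optional, needs an IDE supplement or amendment, and would follow sight of 22+ month outcomes.

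**Conclusion.** The point holds at modest size. The ASES interval is sound but gives up some precision: nothing at r = 0.1 if sites do not differ, and 0.1 to 0.6 points of half-width at assumed correlations of 0.2–0.5 before site terms. The benefit shows mainly at a true deficit such as −3 points.

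The bilateral question is an unresolved ambiguity with the larger potential consequence, because it touches all three co-primaries. A reader might infer that the plan removes bilateral shoulders, or that radiographic power will fall to 79%. The documents do not support either. Removal is implied, not stated. The 79% needs an assumed 30% bilateral share, a fired trigger and no replacement. On the reading in which all shoulders decide, the laterality tests leave the 5% error unchanged.

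The sizes rest on assumed baseline correlation, site ICC and bilateral share. The type I error and binary trigger figures in steps 5 and 6 also treat bilateral shoulders as independent.

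**What to change.** - Make the primary ASES analysis an ANCOVA of the 22+ month score on treatment, pre-operative ASES and site, with a one-sided 95% lower bound against −9.5. Show the unadjusted interval alongside.
- Fix in advance a rule for pooling small sites. The rule under Protocol Deviations, now used only there, could be reused.
- Reconcile Analysis Population with Tests for Interaction: state that all shoulders decide all three co-primaries whatever the laterality tests show, and that those tests and unilateral-only results are sensitivity analyses. The extra unilateral enrolment is then not needed for the primary analysis.

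The cost is SAP wording and one standard model, with no new data. Approvals follow Anticipated Changes (IRB or Ethics Committee and, if necessary, FDA). The statistical downside is an interval about 1% wider if neither baseline nor site is predictive. The change does not itself model correlation between a patient's two shoulders; the simulations in step 4 suggest that this matters little under separate randomisation. If only one part is adopted, it should be the reconciliation.

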Missing Data: Patients who refuse to return for follow-up or who cannot be located and/or do not formally withdraw consent are described as "missing data." Sites will be instructed to continue efforts to contact these patients. See Statistical Plan for more information on how missing data will be handled in the analysis.

Osteolysis: As defined in Exhibit 3: Radiographic Protocol.

Other Interventions: This category includes other surgeries the patient incurs while enrolled in the study that are seemingly unrelated to the implanted device. This would include surgeries such as cholecystectomy, appendectomy, coronary artery bypass surgery, etc.

Revision: A procedure that removes part of the original implant configuration, with or without replacement of the entire component configuration.

Removal: A procedure where the entire original system configuration is removed.

Reoperation: Any surgical procedure that does not include removal or revision, for example, drainage of a hematoma at the surgical site.

Screen Failure: A patient who is either screened but not consented, consented but not randomized or randomized but does not receive the investigational or control device.

Adverse Event (AE): Any event occurring in a study subject that, in the opinion of an M.D. or other qualified and trained medical professional, represents an untoward medical occurrence that differs in either nature, severity, or frequency from a normal post-operative finding. AEs may not have an apparent causal relationship with the device. An AE can therefore be any discrete or ongoing unfavorable and unintended sign (including an abnormal laboratory finding), symptom, or disease temporally associated with the use of a product.

Serious Adverse Event: Any untoward medical occurrence that:

- Results in death
- Is life-threatening
- Requires in-patient hospitalization* or prolongation of existing hospitalization
- Results in persistent or significant disability/incapacity
- Results in congenital anomaly/birth defect

*A planned hospitalization for a pre-existing condition, or a procedure required by the protocol, without a serious deterioration in health is not considered to be a serious adverse event.

Unanticipated Adverse Device Event: any serious adverse event that is or may possibly be related to the device other than those listed in Section C: Risk Analysis or in the institution's approved Informed Consent.

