Theoretically Due: The number of implants that could be examined if all subjects returned on the first day of the follow-up window based on their respective initial surgery dates and the date of database closure.

Deaths: The number of deaths that have taken place in the course of the investigation according to scheduled follow-up visits.

Revisions: The number of revisions that have taken place in the course of the investigational study recorded according to the scheduled follow-up visit.

Withdrawal of Consent: The number of subjects that have withdrawn during the course of the investigational study recorded according to the scheduled follow-up visit.

Not Yet Overdue: Subjects in this category are those who have not yet been evaluated but who are still within the evaluation time window at the time of database closure.

Actual^A: The number of subjects with complete data (i.e. all primary outcomes can be determined) who are actually evaluated within the protocol-defined follow-up intervals.

Actual^B: The number of subjects with any follow-up data (in- or out-of-window) reviewed or evaluated by investigator ("all evaluated" accounting).

Expected: This element is the number of subjects expected for a given time interval. These include the theoretical number of subjects who are due to be evaluated, less the number of subjects who have died, withdrawn, been revised, or are not yet overdue in this time interval.

Follow-up Rate: This element is the ratio of actual subjects evaluated to expected subjects, expressed as a percentage.

MODELS FOR CONTINUOUS MEASURES

Comparisons of Investigational vs Control with regard to continuous baseline and secondary outcomes will be performed using standard statistical tests and will be chosen as appropriate for the scale and distribution of the measures being analyzed. A t-test, Wilcoxon test, or oneway ANOVA (as appropriate) will be performed to assess differences.

CATEGORICAL DATA ANALYSES

Comparisons of Investigational vs Control with regard to categorical baseline, secondary and safety outcomes will be performed using standard statistical tests and will be chosen as appropriate for the scale and distribution of the measures being analyzed. Specifically, categorical outcomes will be compared for investigational and control groups using the Fisher's Exact test (for 2x2 tables) or the Likelihood Ratio chi-square test (for tables larger than 2x2).

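### SANE, Constant and secondary ASES are compared visit by visit on observed scores with no missing-data provision; a repeated-measures model would guard cheaply against dropout that depends on earlier scores differently in the two arms

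*Combined protocol and SAP*

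**What the plan says.** Under Efficacy Evaluations, Secondary Endpoints, the SAP states: "Secondary outcomes include the ASES score, SANE score, Constant score, and radiographic endpoints at 6 weeks, 6 months, 1 year, and 2 years separately". It continues: "These outcomes will be compared for Investigational and Control groups at each time point". The tests are named under Models for Continuous Measures: "A t-test, Wilcoxon test, or oneway ANOVA (as appropriate) will be performed to assess differences". No analysis population and no longitudinal model is given for these scores.

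The missing-data provisions are tied to the primary endpoints:

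- Missing Data and Sensitivity Analyses defines data as missing "for a given primary endpoint if this endpoint cannot be calculated or is not available for a subject in the All Enrolled population".
- The same section then says: "Sensitivity analyses will examine the sensitivity of the results to missing values of the primary outcomes using the following analyses". The table that follows names Radiographic Success, Absence of Revision/Removal and ASES.
- The All Enrolled Population section provides imputation for patients who are "missing data necessary for the determination of any of the co-primary endpoints at 22+ months, data will be imputed as described below".

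The Missing Data definition in the protocol glossary points the reader onward: "See Statistical Plan for more information on how missing data will be handled in the analysis". The plan it points to has no rule for Constant or SANE.

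Three other provisions bear on the point. Under Discontinuations and Revisions, follow-up ends once all components or the humeral stem have been removed. The score to be collected before a revision, where possible, is ASES only. Under Significance Levels, secondary endpoints are reported as exploratory, without claims of significance.

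**The concern.** Separate t-tests or Wilcoxon tests with no imputation can use only the scores observed at each visit. A comparison of observed 2-year scores is safe if loss is unrelated to outcome, or if the loss acts alike in both arms. If one arm preferentially loses patients who were doing badly at 1 year, that arm's remaining mean rises and it looks better than it is. An exploratory label limits what may be claimed from the result but does not remove the shift from the reported estimate. The protocol's Purpose section also lists SANE and Constant among the data by which safety and efficacy are measured.

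The information that could correct for this is already collected. Each score is recorded several times on the same shoulder, so a model using all visits can draw on the earlier scores of those who later leave. The planned by-visit tests discard that information.

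**Working it through.** **1. The plan's own figures.** The documents give no figure for the Constant or SANE analyses, so the check starts from the sample size. Non-inferiority with 93% success in both arms, a 10-point margin, one-sided 5% and 90% power gives

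n = (1.645 + 1.282)² × 2 × 0.93 × 0.07 / 0.10² ≈ 112 per arm.

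Allowing for 15% attrition, 112 / 0.85 = 131.8, or 132 per arm. Both figures match the plan.

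**2. Inputs for the illustration.**

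| Input | Value | Source |
|---|---|---|
| Shoulders per arm | 132 randomised, about 112 observed at 2 years | Sample Size Calculation |
| Missing at 2 years | 15% | The plan's attrition allowance, assumed here to be the realised rate |
| SD | 19 points | The plan's ASES figure; none is given for Constant or SANE, so this is an assumption |
| 1-year to 2-year correlation, ρ | 0.5 to 0.7 | Assumption |
| Dropout slope | Log-odds higher by 0.5, 1.0 or 1.5 per SD lower 1-year score, in one arm only; random in the other | Assumption |
| True difference | 0 | Assumption |

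**3. Formula.** Let m be the mean standardised 1-year score among those who stay. With bivariate normal scores, the observed 2-year mean in the affected arm is too high by ρ × 19 × m. Setting the logistic intercept so that 15% are lost gives, by numerical integration, m = 0.073, 0.133 and 0.175 for slopes 0.5, 1.0 and 1.5.

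The standard error of the observed difference is 19 × √(2/112) = 2.54 points.

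**4. Results, affected arm minus the other arm.**

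| Slope | Shift, ρ = 0.5 | Shift, ρ = 0.7 | Shift in standard errors |
|---|---|---|---|
| 0.5 | 0.5 × 19 × 0.073 = 0.7 | 0.7 × 19 × 0.073 = 1.0 | 0.3 to 0.4 |
| 1.0 | 0.5 × 19 × 0.133 = 1.3 | 0.7 × 19 × 0.133 = 1.8 | 0.5 to 0.7 |
| 1.5 | 0.5 × 19 × 0.175 = 1.7 | 0.7 × 19 × 0.175 = 2.3 | 0.7 to 0.9 |

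Simulation of 4,000 trials per setting gave 0.65, 1.28 and 1.67 points at ρ = 0.5, and 0.94, 1.78 and 2.28 at ρ = 0.7. The nominal 5% test rejected in 6% to 15% of trials.

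**5. Other dropout patterns.**

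- Same rate and same mechanism in both arms: about zero.
- Both arms score-dependent, slopes 1.5 and 0.5, 15% lost in each: 1.7 − 0.7 = 1.0 points at ρ = 0.5, and 2.3 − 1.0 ≈ 1.4 at ρ = 0.7 (2.33 − 0.97 before rounding).
- Slope 1.0 in both arms but unequal rates, ρ = 0.5 to 0.8: 0.8 to 1.3 points at 20% against 10% lost, and 1.6 to 2.5 points at 25% against 5%.

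**6. Effect of using the earlier score.** In the setting of step 4, a likelihood-based repeated-measures estimate had bias within 0.04 points and rejected in 4.5% to 5.8% of trials. Its standard deviation across trials was 2.42 to 2.52, against 2.47 to 2.60 for the observed-score comparison. This result is favourable by construction, because dropout was made to depend only on the observed 1-year score, which is what the model assumes.

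**The case against.** The strongest reply is that nothing rests on these comparisons. Study success depends on the three co-primary endpoints, secondary results carry no significance claim, and the plan openly accepts unadjusted testing over several scores and visits. That stands. The 6% to 15% rejection rate describes a test from which the plan draws no claim, and what remains is a possible shift in a descriptive estimate.

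A reader might infer that the 2-year secondary comparison will be biased. The documents do not support that. Allocation is randomised, patients are to be kept blind up to the 22+ month evaluation, and both arms share one visit schedule. The one outcome-linked loss the plan specifies is the end of follow-up after full or humeral-stem removal. The Risk Analysis says the stemless design may raise the risk of loosening or migration, so a route to unequal loss exists. It is narrow, however, if the plan's assumed 2.0% revision rate is right: 0.02 × 132 is between 2 and 3 shoulders per arm.

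A reader might also infer that the plan has no means of revealing such dropout. That goes too far. Subject Accounting tabulates attendance by arm and visit. The 22+ month ASES, taken from the same shoulders at the same visits, is re-analysed with last observation carried forward, multiple imputation and extreme-value replacement. Those checks could show selective loss and already cover most of what the 2-year secondary ASES would show. They remain indirect for Constant and SANE: they correct neither score, and attendance counts do not show whether those who left had been doing badly.

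**Conclusion.** The gap holds as a matter of method: by-visit tests on observed scores, with no missing-data provision for SANE or Constant, and none for ASES outside the 22+ month primary endpoint. The bias is conditional. It needs dropout that depends on earlier scores and does so differently by arm. Under the assumptions in step 2 it is about 0.7 to 2.3 points, less than one standard error; it is 1.0 to 1.4 points if both arms are affected with slopes 1.5 and 0.5, and about zero if rate and mechanism are the same.

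More extreme dropout gives more. If exactly the worst 25% of one arm and the worst 5% of the other were lost, with ρ = 0.8, simulation gives 4.8 points. Nothing in the documents suggests that pattern. The SD, the correlation and the slopes are assumptions, and 15% is an allowance for possible attrition, not a forecast of loss on these scores. The point is a worthwhile low-cost improvement and has no bearing on study success.

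**What to change.** In the Secondary Endpoints section, specify one mixed model for repeated measures for each of SANE, Constant and secondary ASES:

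- **Population:** all randomised shoulders with any eligible post-operative score.
- **Terms:** arm, visit, arm by visit, site, and the pre-operative score where collected. The visit table has one for ASES and Constant but none for SANE.
- **Covariance:** unstructured over visits, with an allowance for two shoulders from one patient, since randomisation and counting are per shoulder.
- **6-week Constant:** exclude it, as the protocol's own list of secondary endpoints does. Strength and range of motion are not completed at that visit.
- **After full or humeral-stem removal:** state how the missing scores are treated in the analysis, for example with a sensitivity analysis that assigns them a poor value. Otherwise the model implicitly predicts scores as if follow-up had continued without removal.
- **Reporting:** arm difference and confidence interval at each visit, with by-visit means kept as description.

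Before the visits in the model can be fixed, the 6-month time point in the SAP's Secondary Endpoints section must be reconciled with the 3-month visit in the follow-up schedule and the analysis windows.

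The cost is SAP wording and modest programming on data already collected. The limitation is that the model assumes dropout depends only on observed scores.
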